#### **4.6.2. Benefit Assessment**

Subjects participating in this study may experience improvements, whether it is due to GSK2981278 or the vehicle, in their psoriasis lesions during the course of the study.

Subjects may also benefit from the overall health assessment conducted while participating in this study. Subjects participating in the study will also contribute to the process of developing a novel agent for the topical treatment of plaque psoriasis.

#### **4.6.3. Overall Benefit:Risk Conclusion**

Taking into account the measures taken to minimize risk to subjects participating in this study, the potential risks identified in association with GSK2981278 ointment are justified by the anticipated benefits that may eventually be afforded to subjects with plaque psoriasis.

### **5. SELECTION OF STUDY POPULATION AND WITHDRAWAL CRITERIA**

Specific information regarding warnings, precautions, contraindications, adverse events, and other pertinent information on the GSK investigational product or other study treatment that may impact subject eligibility is provided in the IB.

Deviations from inclusion and exclusion criteria are not allowed because they can potentially jeopardize the scientific integrity of the study, regulatory acceptability or subject safety. Therefore, adherence to the criteria as specified in the protocol is essential.

The selection of subjects is in accordance with the requirements of §§ 40 and 41 of the German drug law (AMG) as well as the recommendations of the currently valid revision of the Helsinki Declaration and the International conference on harmonisation of technical requirements for registration of pharmaceuticals for human use (ICH)-Good Clinical Practice (GCP) guideline.

#### **5.1. Inclusion Criteria**

A subject will be eligible for inclusion in this study only if all of the following criteria apply:

AGE
1. 18 years of age and above, at the time of signing the informed consent.
TYPE OF SUBJECT AND DIAGNOSIS INCLUDING DISEASE SEVERITY
2. Subjects with clinical diagnosis of stable plaque psoriasis for $\geq 6$ months, as confirmed by the investigator. 3. Body surface area involvement $\geq 5\%$ and $\leq 15\%$ , excluding face and intertriginous areas, at Screening and Baseline ( Appendix 2 ). The area of psoriasis involvement may include up to 2% of total BSA on the scalp with only sparse terminal hair and/or vellus hair.

4. A PGA score of <math>\geq 2</math> at Baseline (Appendix 3)
 
5. One target plaque located on the trunk or proximal parts of extremities (excluding scalp, knees, and elbows) that is at least <math>9 \text{ cm}^2</math> in size at Screening and Baseline with a Target Plaque Severity Score (TPSS) <math>\geq 5</math> and induration subscore <math>\geq 2</math>. (Appendix 4)

--

SEX
-----

6. Male

Male subjects with female partners of child bearing potential must comply with the following contraception requirements from the time of first dose of study medication until 2 weeks after the last dose of study medication.

- Vasectomy with documentation of azoospermia. The documentation on male sterility can come from the site personnel's: review of subject's medical records, medical examination and/or semen analysis, or medical history interview.

- Male condom

The allowed method of contraception is only effective when used consistently, correctly and in accordance with the product label. The investigator is responsible for ensuring that subjects understand how to properly use these methods of contraception.

7. Female of non-reproductive potential (FNRP)

A FNRP is eligible to participate in this study if she meets at least one of the following conditions:

- Females with one of the following procedures documented and no plans to utilize assisted reproductive techniques (e.g., in vitro fertilization or donor embryo transfer):

- Bilateral tubal ligation or salpingectomy
- Hysteroscopic tubal occlusion procedure with follow-up confirmation of bilateral tubal occlusion
- Hysterectomy
- Bilateral Oophorectomy (surgical menopause)

- Post-menopausal women (including all women over 60 years of age, see below),

Post-Menopause criteria

- Females 60 years of age or older
- A practical definition accepts menopause after 1 year without menses with an appropriate clinical profile, e.g., age appropriate,  $>45$  years, in the absence of hormone replacement therapy (HRT) or medical suppression of the menstrual cycle (e.g., leuprolide treatment).
  - In questionable cases for women  $<60$  years of age, a blood sample with simultaneous follicle stimulating hormone and estradiol falling into the central laboratory's post-menopausal reference range is confirmatory (these

levels need to be adjusted for specific laboratories/assays) [Kronenberg, 2008; Strauss, 2004].

- Females under 60 years of age, who are on HRT and wish to continue, and whose menopausal status is in doubt, should not be enrolled in this study. Otherwise, they must discontinue HRT to allow confirmation of post-menopausal status prior to study enrollment. For most forms of HRT, at least 2 to 4 weeks will elapse between the cessation of therapy and the blood draw; this interval depends on the type and dosage of HRT. Following confirmation of their post-menopausal status, they can enrol into the study and resume use of HRT.

#### INFORMED CONSENT

8. Capable of giving signed informed consent which includes compliance with the requirements and restrictions listed in the consent form and in this protocol.

#### 5.2. Exclusion Criteria

A subject will not be eligible for inclusion in this study if any of the following criteria apply:

#### CONCURRENT CONDITIONS/MEDICAL HISTORY (INCLUDES LIVER FUNCTION AND QTc INTERVAL)

1. Psoriasis other than plaque variant (i.e. acute psoriasis guttate, psoriasis punctata, psoriasis erythroderma or pustular psoriasis).
2. Current evidence of another ongoing or any acute cutaneous infection, history of repeated or chronic significant skin infections (unless irrelevant in the opinion of the investigator, i.e. onychomycosis, labial herpes or other minor diagnosis).
3. Clinically-relevant skin disease or other skin pathologies, that may, in the opinion of the investigator, contraindicate participation or interfere with skin evaluations.
4. Alanine aminotransferase (ALT)  $>2 \times$ ULN and bilirubin  $>1.5 \times$  upper limit of normal (ULN) (isolated bilirubin  $>1.5 \times$ ULN is acceptable if bilirubin is fractionated and direct bilirubin  $<35\%$ ).
5. Current or chronic history of liver disease, or known hepatic or biliary abnormalities (with the exception of Gilbert's syndrome or asymptomatic gallstones)
6. QTcB  $>450$  msec or QTcB  $>480$  msec in subjects with Bundle Branch Block. The QTcB should be based on single QTcB values of ECG obtained over a brief recording period. If QTcB is outside the threshold value, triplicate ECGs may be performed with the QTcB values averaged.
7. Any condition that, in the judgement of the investigator, would put the subject at unacceptable risk for the participation in the trial.
8. History of malignancy within 5 years prior to dosing, except adequately treated non-invasive cancer of the skin (basal or squamous cell).

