## DIAGNOSTIC ASSESSMENTS AND OTHER CRITERIA

12. Presence of hepatitis B surface antigen (HBsAg), positive hepatitis C antibody test result at screening or within 3 months prior to first dose of study treatment.

13. A positive pre-study drug/alcohol screen.

14. A positive test for human immunodeficiency virus (HIV) antibody.

15. **For Part B only**-the subject has participated in Part A of this study.

16. The subject has participated in a clinical trial and has received an investigational product within the following time period prior to the first dosing day in the current study: 4 weeks, 5 half-lives or twice the duration of the biological effect of the investigational product (whichever is longer).

17. Prolonged exposure to natural or artificial sources of ultraviolet (UV) radiation (e.g., exposure to sunlight other than that associated with usual daily activities, use of tanning booth, etc.) within 2 weeks prior to the Day 1 visit or intention to have such exposure during the study, thought by the investigator likely to modify the subject's psoriasis.

18. In the opinion of the investigator or physician performing the initial examination the subject should not participate in the clinical trial, e.g. due to probable noncompliance, inability to understand the trial and give adequately informed consent, or inability to complete the Psoriasis Symptom Diary ([Appendix 5](#)).

19. Close affiliation with the investigator (e.g. a close relative) or persons working at bioskin GmbH or subject is an employee of sponsor.

20. Subject is institutionalized because of legal or regulatory order.

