### 5.4.1.1. Study Treatment Restart or Rechallenge

Study treatment restart or rechallenge after liver chemistry stopping criteria are met by any subject participating in this study is not allowed.

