## Phase II liver chemistry increased monitoring criteria with continued therapy

[figure not shown]
Liver Chemistry Increased Monitoring Criteria – Liver Monitoring Event	
Criteria	Actions
ALT $\geq$ 3xULN and <5xULN and bilirubin <2xULN, without symptoms believed to be related to liver injury or hypersensitivity, and who can be monitored weekly for 4 weeks	
 
Notify the GSK medical monitor within 24 hours of learning of the abnormality to discuss subject safety.
 
Subject can continue study treatment
 
Subject must return weekly for repeat liver chemistries (ALT, AST, alkaline phosphatase, bilirubin) until they resolve, stabilize or return to within baseline
 
If at any time subject meets the liver chemistry stopping criteria, proceed as described above
 
If, after 4 weeks of monitoring, ALT <3xULN and bilirubin <2xULN, monitor subjects twice monthly until liver chemistries normalize or return to within baseline.
 

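### Exclusion criterion 4 joins its ALT and bilirubin limits with *and*: read literally, no numeric criterion keeps out a subject with isolated ALT above 2×ULN, and the criterion's own bilirubin exception has nothing to except

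*Protocol*

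**What the plan says.** Protocol Section 5.2 makes each numbered exclusion sufficient on its own: "A subject will not be eligible for inclusion in this study if any of the following criteria apply". Criterion 4 is the only one with numeric liver limits. It names ALT >2×ULN and bilirubin >1.5×ULN, joined by *and*. A parenthesis then says that an isolated bilirubin >1.5×ULN "is acceptable if bilirubin is fractionated and direct bilirubin" is <35%.

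Section 5 forbids deviations from the eligibility criteria and states that "adherence to the criteria as specified in the protocol is essential".

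The other ALT limits are on-treatment rules in Appendix 6:
- ALT ≥5×ULN is a stopping event, with immediate discontinuation. Section 5.4.1.1 adds: "Study treatment restart or rechallenge after liver chemistry stopping criteria are met by any subject participating in this study is not allowed".
- ALT of 3 to <5×ULN with bilirubin <2×ULN and no related symptoms is a monitoring event. Treatment may continue, but "Subject must return weekly for repeat liver chemistries".

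**The concern.** The two halves of criterion 4 do not fit together. With *and*, a subject is excluded only when both values are raised, so a subject with raised bilirubin alone never meets the criterion and needs no exemption. The exemption makes sense only if raised bilirubin alone can exclude, which means *or*.

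At stake is a safety threshold at entry. Followed as written, criterion 4 lets through any isolated ALT elevation, including values at which the same protocol orders weekly liver tests or permanent discontinuation. It also lets through isolated bilirubin elevation with a high direct fraction, which the parenthesis appears meant to keep out.

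**Working it through.** The protocol states no figure to reproduce; the check is one of logic and cross-reading.

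**Inputs.** From Section 5.2, criterion 4: limit A is ALT >2×ULN, limit B is bilirubin >1.5×ULN, the connector is *and*, and the exception is B without A with direct bilirubin <35%. From Section 5.2, opening line: any one criterion excludes. From Appendix 6: the 3×ULN and 5×ULN ALT levels.

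**Step 1: list the combinations and apply both readings.**

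| Combination | Literal: A *and* B | A *or* B, with exception |
|---|---|---|
| (a) Neither raised | eligible | eligible |
| (b) ALT only | eligible | excluded |
| (c) Bilirubin only, direct <35% | eligible | eligible |
| (d) Bilirubin only, direct ≥35% | eligible | excluded |
| (e) Both raised | excluded | excluded |

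The literal reading excludes {e}, 1 of 5. The *or* reading excludes {b, d, e}, 3 of 5. They differ in {b, d}, 2 of 5.

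**Step 2: test whether the exception does anything.** Take all 2 × 2 × 2 = 8 cells of ALT raised or not, bilirubin raised or not, and direct fraction below 35% or not. Adding the exception changes 0 of 8 outcomes under *and*. Under *or* it changes 1 of 8: isolated bilirubin with direct <35% moves from excluded to eligible. The exception works only under *or*.

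**Step 3: see how the protocol uses the two words elsewhere.** Where ALT is paired with bilirubin in the Appendix 6 stopping criteria and in the liver item of the serious adverse event definition (Section 12.8.2), *and* means both together. Where alternatives are meant, the text says *or*: criterion 6 on QTcB, two items further on, and the QTc stopping rule in Section 5.4.2. A site reading consistently would take criterion 4 to require both.

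**Step 4: look for another numeric barrier.** There is none.
- Criterion 5 covers liver disease and known hepatic or biliary abnormalities, without a laboratory limit.
- Criterion 12 is hepatitis serology, and criterion 13 is the drug and alcohol screen.
- Criterion 7 is investigator judgement on whether a condition "would put the subject at unacceptable risk for the participation in the trial".
- Criterion 18 is also judgement: "In the opinion of the investigator or physician performing the initial examination the subject should not participate in the clinical trial".

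**Step 5: follow combination (b) into treatment.** Bilirubin is at most 1.5×ULN here, so the <2×ULN condition of the monitoring rule is already met.

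| ALT with bilirubin not raised | Criterion 4, literal | Appendix 6 on treatment |
|---|---|---|
| >2 to <3×ULN | not excluded | no action |
| 3 to <5×ULN, no symptoms | not excluded | weekly liver chemistry |
| ≥5×ULN | not excluded | immediate stop, no restart |

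**The case against.** The strongest reply is that the intended meaning can be recovered from the sentence itself. The parenthesis implies that bilirubin alone excludes, so a sensible investigator would read two separate limits with one exception and would probably turn away combination (d). On that view only isolated ALT is a solid gap. Criterion 5 is also broader than a list of named diseases: an unexplained ALT ≥5×ULN at Screening could count as a known hepatic abnormality by Day 1, when eligibility is checked again. Criteria 7 and 18 are criteria as specified too, so using them is no deviation. If such a subject were dosed, liver chemistry is repeated on Days 15, 29 and 57, and Appendix 6 would act.

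Much of this stands as a limit on harm. Dosing a subject with ALT ≥5×ULN would mean passing over several discretionary safeguards, and the count of 2 in 5 is of logical cases, not of patients. But reading the sentence sensibly means departing from its connector, and the protocol uses *and* for ALT with bilirubin elsewhere to mean both. A qualitative or discretionary criterion does not replace the numeric limit that criterion 4 sets out to give.

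**Conclusion.** The concern holds. Criterion 4 is wrong as written: its connector and its exception cannot both be meant. The literal text excludes 1 of 5 combinations, against 3 of 5 under the only reading that gives every part of the sentence a function. The firmer of the two gaps is isolated ALT >2×ULN without an upper bound; isolated bilirubin with direct fraction ≥35% is the second.

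The conclusion rests on the literal text, which Section 5 says must be followed, and on the absence of any other ALT or bilirubin limit among the eligibility criteria. The protocol gives no frequency of isolated ALT elevation in this population, so nothing can be said about how many of the 8 + 18 = 26 planned subjects might be affected. No effect on endpoints, estimates or sample size is claimed. The severity is minor.

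**What to change.** In Section 5.2, criterion 4, change the connector between the two limits from *and* to *or*, so that it excludes ALT >2×ULN *or* bilirubin >1.5×ULN, and keep the parenthesis on isolated bilirubin unchanged. Isolated ALT elevation is then excluded. Isolated bilirubin elevation is excluded unless fractionated with direct bilirubin <35%, and both raised together remains excluded.

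This is a one-word protocol change. ALT and total and direct bilirubin are already in the safety panel (Section 7.5.6, Table 4), which is drawn at Screening in both parts (Sections 7.1 and 7.2), so no test or visit is added. The cost is at most a few more screen failures.

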## CONCOMITANT MEDICATIONS

9. Use of prohibited concomitant medications or products within the defined periods before the Day 1 visit and during the trial ([Table 2](#)).

## CONTRAINDICATIONS

10. History of sensitivity to any of the study medications, or components thereof or a history of drug or other allergy that, in the opinion of the investigator or Medical Monitor, contraindicates their participation.

11. Symptoms of a clinically significant illness that may, in the opinion of the investigator, influence the outcome of the trial in the 4 weeks before baseline visit and during the trial.

## DIAGNOSTIC ASSESSMENTS AND OTHER CRITERIA

12. Presence of hepatitis B surface antigen (HBsAg), positive hepatitis C antibody test result at screening or within 3 months prior to first dose of study treatment.

13. A positive pre-study drug/alcohol screen.

14. A positive test for human immunodeficiency virus (HIV) antibody.

15. **For Part B only**-the subject has participated in Part A of this study.

16. The subject has participated in a clinical trial and has received an investigational product within the following time period prior to the first dosing day in the current study: 4 weeks, 5 half-lives or twice the duration of the biological effect of the investigational product (whichever is longer).

17. Prolonged exposure to natural or artificial sources of ultraviolet (UV) radiation (e.g., exposure to sunlight other than that associated with usual daily activities, use of tanning booth, etc.) within 2 weeks prior to the Day 1 visit or intention to have such exposure during the study, thought by the investigator likely to modify the subject's psoriasis.

18. In the opinion of the investigator or physician performing the initial examination the subject should not participate in the clinical trial, e.g. due to probable noncompliance, inability to understand the trial and give adequately informed consent, or inability to complete the Psoriasis Symptom Diary ([Appendix 5](#)).

19. Close affiliation with the investigator (e.g. a close relative) or persons working at bioskin GmbH or subject is an employee of sponsor.

20. Subject is institutionalized because of legal or regulatory order.

### 5.3. Screening/Baseline/Run-in Failures

Screen failures are defined as subjects who consent to participate in the clinical trial but are never subsequently randomized. In order to ensure transparent reporting of screen failure subjects, meet the Consolidated Standards of Reporting Trials (CONSORT) publishing requirements, and respond to queries from Regulatory authorities, a minimal set of screen failure information is required including Demography, Screen Failure details, Eligibility Criteria, and Serious Adverse Events (Section 7.5.1.5).

Subjects who initially do not meet eligibility criteria (e.g., due to use of prohibited concomitant medications requiring a longer washout than the specified screening period) may be re-screened for the same Part of the study once if their potential eligibility status has changed. Eligible subjects may then be enrolled in the study.

A subject who previously failed screening for Part A may be re-screened for Part B if the investigator considers that the subject's potential eligibility status has changed.

### 5.4. Withdrawal/Stopping Criteria

Study treatment will be stopped and the subject will complete the Day 57 assessments and subsequently enter the follow-up period if any of the following stopping criteria are met:

- Subject experiences an AE that is severe enough in nature to warrant treatment discontinuation in the opinion of the investigator.
- Subject presents with a worsening of psoriasis that requires treatment with a prohibited concomitant medication in the opinion of the investigator (Table 2).
- Additional for **Part B**: The subject's randomized treatment assignment is unblinded by the investigator.

Reasons for withdrawal from the study may include but are not limited to the following:

- Withdrawal of consent. If specified by the subject, the investigator should document the reason for withdrawal of consent.
- Noncompliance with study procedures
- Lost to follow-up
- Termination of study by sponsor
- Protocol deviation
- Investigator discretion

The following actions must be taken in relation to a subject who fails to attend the clinic for a required study visit:

- The site must attempt to contact the subject and re-schedule the missed visit as soon as possible.

- The site must counsel the subject on the importance of maintaining the assigned visit schedule and ascertain whether or not the subject wishes to and/or should continue in the study.
- In cases where the subject is deemed 'lost to follow-up', the investigator or designee must make every effort to regain contact with the subject (where possible, 3 telephone calls and if necessary a certified letter to the subject's last known mailing address or local equivalent methods). These contact attempts should be documented in the subject's medical record.
- Should the subject continue to be unreachable, only then will he/she be considered to have withdrawn from the study with a primary reason of "Lost to Follow-up".

A subject may withdraw from study treatment or the study at any time at his/her own request, or may be withdrawn at any time at the discretion of the investigator for safety, behavioural or administrative reasons. If a subject withdraws from the study, he/she may request destruction of any samples taken, and the investigator must document this in the site study records. If the subject has not withdrawn consent to participate in the study, then the Week 8 assessments should be performed at the time a subject is prematurely withdrawn from the treatment.

[figure not shown]
If a subject prematurely withdraws prior to enrollment in **Part A** or randomization in **Part B**, this subject will be classed as a screen failure and will not be counted towards the planned enrollment target. The primary reason for withdrawal from the study must be recorded in the eCRF.

#### **5.4.1. Liver Chemistry Stopping Criteria**

**Liver chemistry stopping and increased monitoring criteria** have been designed to assure subject safety and evaluate liver event etiology (in alignment with the FDA premarketing clinical liver safety guidance).

<http://www.fda.gov/downloads/Drugs/GuidanceComplianceRegulatoryInformation/Guidances/UCM174090.pdf>

## Phase II Liver Chemistry Stopping and Increased Monitoring Algorithm

Liver Safety Required Actions and Follow-up Assessments Section can be found in [Appendix 6](#).

